### **Objectives**

The objectives of this study are to investigate the effect of regular vigorous aerobic exercise training of running on motor and non-motor symptoms, and quality-of-life of people with Parkinson's disease.

### **Background and purpose**

There is a growing volume of evidences support the positive effect of exercise and physical therapy to Parkinson's disease. Various exercise types have shown different positive effects. Gait training for 4 weeks showed a moderate improvement in balancing while balance training of 8 to 26 weeks decreased fall rate. Cued exercise would mildly increase the speed of the gait. Complementary exercises, such as Tai Chi and dancing, have shown improvement in balancing of the patients.

One of the main complaints of Parkinson's disease is rigidity. It is because of the musculoskeletal impairments which compromise the flexibility and stability of both axial structure (spine) and the extremities. Truncal stiffness and rigidity results in a stooped posture, which further undermines one's balance and agility. Flexibility training (stretching) is shown to be beneficial to all stages of patients with Parkinson's disease, in terms of improved both range of movement in joints and spinal stability. It is recommended that regular stretching should be the first step in one's exercise program to combat the muscle rigidity. High quality clinical trial and meta-analysis have demonstrated short term, and to a lesser extent, long term benefits in various outcome measures. To achieve positive effects, supervised progressive strength and aerobic endurance training program of 12 weeks was required. Extended progressive strength training improved muscle strength for up to 24 months. While aerobic endurance training would increase walking capacity up to 16 months.

There are data suggested a threshold of intensity of exercise to be reached for the positive effect. This overall body of evidence suggests that regular vigorous exercise should be accorded a central place in the treatment of Parkinson's disease.

However, there was no evidence about regular intensive exercise of running in Parkinson's disease. And most of the studies were not randomized with a control group.

### **Study design**

Prospective randomized controlled, single-blind study

### **Inclusion criteria**

1. Patient with idiopathic Parkinson's disease, aging from 40 years to 60 years old.
2. Patient should be able to walk independently without walking aids for a distance of 30 meters.

### **Exclusion criteria**

1. Previous history of other neuro-degenerative diseases
2. Presence of ischemic heart disease or musculoskeletal and cardiopulmonary diseases
3. Presence of physical disability
4. History of regular running practice in the past 6 months.

### **Method**

This is a prospective randomized controlled single-blinded study. 30 patients will be included and randomized to intervention arm or control arm in a ratio of 2 to 1. Informed consent will be signed after the patient is fully informed about the procedures and prior to the baseline assessments.

Intervention arm

- Number of participants: 20
- Venue: Shatin playground
- Supervisors: licensed coaches (2 to 4 per session)
- Training session:
  - 30 minutes of warm-up stretching
  - 60 minutes supervised progressive aerobic endurance track running 
- Targeted intensity:
  - 60-75% of maximum heart rate ( $HR_{max} = 220 - age$ ) OR
  - 40-50% heart rate reserve ( $HRR = HR_{max} - HR_{rest}$ )
- Frequency and training period: 2 sessions per week, for 24 weeks

Control arm

- Number of participants: 10
- Venue: Indoor gymnasium
- Supervisor: a physiotherapist
- Training session: 60 minutes of physical stretching
- Frequency and training period: 1 session per week, for 24 weeks

Each participant in either group will be given a diary to record the number of self-practice sessions to measure the exercise compliance; as well as the fall incidence during the whole training period and up to 6-month follow-up after training completion. They will also record any adverse events related to the training such as pain, injury, muscle soreness etc. Compliance and drop-out rate can also be monitored using the diary. The diary will be collected at the end of each month.

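### Do the two heart-rate targets joined by OR leave the intensity of the running programme undefined?

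*Protocol*

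**What the plan says.** Under Method, the running arm has two intensity targets joined by OR: "60-75% of maximum heart rate", with the maximum taken as 220 minus age, and "40-50% heart rate reserve", with the reserve defined as maximum minus resting rate. No resting rate is given, no target is stated in bpm, and nothing says whether a session may meet either target or whether one method is fixed for each participant.

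The Inclusion criteria admit patients "aging from 40 years to 60 years old". The Objectives concern "the effect of regular vigorous aerobic exercise training of running". Background and purpose refers to earlier data pointing to "a threshold of intensity of exercise to be reached for the positive effect" and to a gap in the literature, "no evidence about regular intensive exercise of running". None of these intensity terms carries a number, and the Method section does not use the word vigorous.

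**The concern.** Two alternative targets for the same session suggest two ways of stating one intensity. By the protocol's own formulas they are not: a heart rate can satisfy the first and fall below or above the second. With two to four coaches per session and no stated rule, participants of the same age and resting rate could be held to different ranges.

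Intensity is also part of the rationale. The Background speaks of a threshold and the Objectives name vigorous exercise, yet neither is tied to the prescribed ranges. What would be at stake is interpretation: whether a positive result could be credited to vigorous intensity, or a null result explained by too little of it.

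**Working it through.** **Inputs.** From Method: limits of 60% and 75% of HRmax, limits of 40% and 50% of HRR, HRmax = 220 - age, HRR = HRmax - HRrest. From Inclusion criteria: ages 40 to 60, so HRmax runs from 180 down to 160 bpm. HRrest is not given; I assume 60-80 bpm and look at 50 and 90 as well. There is no stated bpm figure to reproduce.

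**Reading the reserve target.** A working heart rate needs the resting rate added back: HRrest + fraction x HRR. The protocol leaves this step unwritten, but the bare product cannot be meant. At age 50, rest 70, it is 0.40 x 100 = 40 to 0.50 x 100 = 50 bpm, below the resting rate.

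**Can the ranges coincide?**
- Lower limits: 0.60 HRmax = HRrest + 0.40 (HRmax - HRrest) gives HRrest = HRmax/3.
- Upper limits: 0.75 HRmax = HRrest + 0.50 (HRmax - HRrest) gives HRrest = HRmax/2.
- Both cannot hold for one person, so the ranges are never identical.
- Widths: 0.15 HRmax against 0.10 (HRmax - HRrest). The ratio is 1.5 x HRmax/(HRmax - HRrest), which exceeds 1.5 for any resting rate.

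**Numbers for the assumed resting rates**

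| Age, rest | HRmax | 60-75% HRmax | 40-50% HRR | Width ratio | Share of first range outside second |
|---|---|---|---|---|---|
| 40, 60 | 180 | 108-135 | 108-120 | 27/12 = 2.25 | 15/27 = 56% |
| 50, 70 | 170 | 102-127.5 | 110-120 | 25.5/10 = 2.55 | 15.5/25.5 = 61% |
| 60, 80 | 160 | 96-120 | 112-120 | 24/8 = 3.0 | 16/24 = 67% |

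The last column is only 1 minus the inverse of the width ratio, so it adds no separate evidence. At age 50, rest 70, the midpoints are (102 + 127.5)/2 = 114.75 and (110 + 120)/2 = 115 bpm: the ranges differ in width, hardly in centre.

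**What OR amounts to if either target suffices.** The reserve range lies inside the HRmax range whenever HRmax/3 <= HRrest <= HRmax/2. The lower bound is 60 bpm at age 40 and 53.3 at age 60; the upper bound is 90 at age 40 and 80 at age 60. Resting rates of 60-80 bpm therefore satisfy the condition at every eligible age, and either-suffices reduces to 60-75% of HRmax.

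Outside that range of resting rates the combined target is slightly wider. At rest 50 the reserve range starts below the other by 108 - 102 = 6 bpm at age 40 and 96 - 94 = 2 bpm at age 60. At rest 90 it ends above the other by 130 - 127.5 = 2.5 bpm at age 50 and 125 - 120 = 5 bpm at age 60. The ranges separate altogether only when 0.40 HRmax + 0.60 HRrest > 0.75 HRmax, that is HRrest > 0.583 HRmax: about 93 bpm at age 60 and 105 bpm at age 40.

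**Does the choice of target reach the analysis?** None of the listed primary or secondary outcomes involves heart rate, and compliance is taken from the diary. No sample-size or power figure depends on it. The arms already differ in activity (track running against stretching), frequency (2 sessions a week against 1), session length (30 + 60 = 90 minutes against 60), venue and supervision. Weekly supervised time is 2 x 90 = 180 minutes against 60. The contrast is programme against programme, whichever heart-rate target is used.

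**The case for a change.** The best case for a change is that the intervention must be defined in the protocol and cannot be left to an analysis plan. If one method is fixed per participant, or chosen by each coach, the delivered intensity may vary for no clinical reason. If either suffices, the reserve line does no work at ordinary resting rates. The protocol describes no record of session heart rate, so delivered intensity could not be recovered afterwards, in a trial whose rationale rests on intensity.

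Part of this stands. The text does not say how the alternative is applied, and the two ranges do differ. A sentence on this would be tidy, but coaches have a workable reading without it. Redundancy of one line is not an error, because percentages of two different bases generally give different ranges and the protocol asserts no equivalence. Choosing one target would not recover delivered intensity either; only recording heart rate would, over up to 20 x 2 x 24 = 960 participant-sessions, which is an added task and not a correction.

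The point about the word vigorous is weaker. A one-sentence objective need not repeat numbers, and Method can be read as its working definition. The threshold sentence describes earlier data and makes no claim about this regimen. To show a contradiction one would need an outside classification of intensity, which the document does not contain.

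**Conclusion.** The arithmetic behind the concern is right, but it exposes no error. The ranges are never identical, with a width ratio above 1.5 at any resting rate and 2.25 to 3.0 at an assumed 60-80 bpm. No stated figure is wrong, and on the natural reading of OR the target is definite: 60-75% of HRmax at those resting rates, extended by at most 6 bpm at the ages and resting rates of 50 and 90 bpm worked above. That simplification rests on the assumed resting rates and on adding the resting rate back; it fails for unusually high values, from about 93 bpm at age 60.

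The randomised comparison is untouched. Attribution to intensity as such is limited by the many other differences between the arms and would remain so with a single target. This is missing detail that those running the sessions can fill sensibly. How the alternative is applied, and the intensity itself, remain the investigator's clinical decision. No change to the plan follows.

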### **Secondary outcomes**

- Endurance: 6-minute walking test; Gait: fastest walking speed; Balance: minibest test
- Non-motor symptoms including depression and mood
- Adverse events: fall incidence (6 months prior to the training, throughout training and follow-up period), injury, muscle soreness and whether medical intervention is required.

The assessment will be taken by two blinded assessors (one occupational therapist and a registered research nurse) at baseline, at completion of the training and 6 months after, at Prince of Wales Hospital.

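### Does the running arm's threefold supervised contact, with a self-reported primary outcome, undermine the objective of studying running?

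*Protocol*

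**What the plan says.** The Objectives section sets out to "investigate the effect of regular vigorous aerobic exercise training of running on motor and non-motor symptoms, and quality-of-life". The Study design section describes a "Prospective randomized controlled, single-blind study", and under Method "30 patients will be included and randomized to intervention arm or control arm in a ratio of 2 to 1", that is, 20 and 10.

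The Method section then defines the arms:

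- **Intervention:** each session has "30 minutes of warm-up stretching" followed by 60 minutes of supervised track running, at a playground, with two to four coaches, for "2 sessions per week, for 24 weeks".
- **Control:** each session is 60 minutes of stretching in an indoor gymnasium with one physiotherapist, for "1 session per week, for 24 weeks".

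The Primary outcomes section names three measures without ranking them: the overall UPDRS, the UPDRS part III motor score and the PDQ-39. On blinding, the Secondary outcomes section says "The assessment will be taken by two blinded assessors (one occupational therapist and a registered research nurse"). Nothing says that participants are blinded, and they could not be.

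**The concern.** The stated interest is "the effect of regular vigorous aerobic exercise training of running", yet the arms differ in more than running. The intervention arm meets twice as often, for longer each time, in a different place and under a different profession. All of these differ completely by arm, so no analysis can separate them from running.

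Lack of participant blinding adds to this. Where the participant supplies the answer, a blinded assessor does not blind the measurement. Someone assigned to a coached running programme may report better quality of life because of expectation or attention, and the PDQ-39 has the same standing as the examiner-rated motor score. At stake is the reading of a positive PDQ-39 result: it could be taken as a physiological effect of vigorous running when part of it came from something else.

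**Working it through.** **Arm sizes (the plan's own derived figure).** 30 × 2/3 = 20 and 30 × 1/3 = 10, as the Method section states.

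**Contact per participant, from the schedules under Method.**

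| | Intervention | Control |
|---|---|---|
| Sessions | 2 × 24 = 48 | 1 × 24 = 24 |
| Minutes per session | 30 + 60 = 90 | 60 |
| Minutes per week | 2 × 90 = 180 | 60 |
| Total contact | 48 × 90 min = 72 h | 24 × 60 min = 24 h |
| of which stretching | 48 × 30 min = 24 h | 24 h |
| of which running | 48 × 60 min = 48 h | 0 h |

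Contact is 72/24 = 3 to 1 and sessions are 2 to 1. If only the 60 minutes explicitly labelled as supervised is counted, contact is 48/24 = 2 to 1.

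**What the excess consists of.** 72 − 24 = 48 h, which equals the running time. Stretching cancels at 24 h in each arm. The contrast is stretching plus supervised running against supervised stretching.

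**Staffing.** Headcount must be set against arm size. If each arm trains as one group with full attendance (an assumption; the protocol does not say), there are 20/4 = 5 to 20/2 = 10 participants per coach in the intervention arm, and 10/1 = 10 per physiotherapist in the control arm. With two coaches the ratios are equal.

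**What matching would involve.** Equal contact means 180 minutes a week in the control arm. If that were filled with stretching, controls would receive 72 h of it against 24 h in the running arm. The Background section regards stretching as beneficial in itself, so matching contact would unbalance an active component that is now balanced. This shows the trade-off and is not a proposal for either schedule.

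**Scale of a possible bias.** The protocol gives no SD and no attention effect. Suppose, purely for illustration, that attention and expectation shift the PDQ-39 by 0.2 to 0.4 SD. With 20 and 10 participants, the half-width of the 95% interval for a difference in means is t(0.975, 28) × √(1/20 + 1/10) = 2.048 × 0.387 = 0.79 SD. That is about two to four times the assumed shift (0.79/0.4 ≈ 2.0; 0.79/0.2 ≈ 4.0). The comparison gives a sense of scale only. A wide interval does not remove a bias, and supervised controls would carry some of the attention effect too.

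**The case for a change.** The strongest case for acting is that the comparator, the objective and the choice of primary outcomes are fixed in the protocol and cannot be repaired in an analysis plan. The Background section also presents a randomised control group as what earlier work mostly lacked, so the control arm has to bear weight. Three inexpensive changes suggest themselves: reword the objective as a programme comparison, rest the efficacy claim on the blinded part III score with the PDQ-39 and overall UPDRS made secondary, and have assessors record their guess of allocation.

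The premises stand: contact is unequal, its components cannot be separated, and the PDQ-39 is open to expectation. None of the three changes gains enough.

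- **Rewording the objective** is editorial. It already speaks of investigating regular training, which describes a programme, and the protocol contains no planned conclusion about running in isolation. No estimate would change.
- **Making the PDQ-39 secondary** is a trade-off. Quality of life is a named objective and would be left without a primary measure. Lack of participant blinding is unavoidable in this kind of trial; it calls for caution but does not disqualify the outcome. The same argument against the overall UPDRS depends on knowledge of the scale that the protocol does not supply. Nor would reliance on part III cure the contact imbalance, which affects the motor score as well.
- **Recording assessors' guesses** tests assessor blinding, which is not in doubt here. It bears on neither contact time nor participant expectation.

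**Conclusion.** No change is needed. The imbalance is real (72 h against 24 h, 48 against 24 sessions), but with stretching equal at 24 h the surplus is the intervention itself. The comparison validly estimates the effect of adding a supervised running programme to stretching. Supervised controls over the same 24 weeks and blinded assessors already give some protection.

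Two limits remain for whoever interprets the results. The estimate belongs to the programme, including its frequency, attention and setting, and not to running alone. The PDQ-39 should be read beside the blinded part III score, with expectation in mind. The size of any such bias cannot be derived from the protocol; the 0.2 to 0.4 SD used above is an assumption. That participants know their arm is inferred from the nature of the two programmes, since the protocol describes blinding only for the assessors.

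### Participants record non-fall adverse events only if they link them to training, a condition the adverse-event outcome does not carry

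*Protocol*

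**What the plan says.** The Protocol's Method section sets up the diary: "Each participant in either group will be given a diary". It holds self-practice sessions and falls, "as well as the fall incidence during the whole training period and up to 6-month follow-up after training completion", and is collected monthly. Falls carry no condition on cause. For everything else the instruction is: "They will also record any adverse events related to the training such as pain, injury, muscle soreness etc".

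Secondary outcomes lists the adverse-event outcome as fall incidence (before training, during it and in follow-up) together with "injury, muscle soreness and whether medical intervention is required". No relatedness condition is stated there. The same section says "The assessment will be taken by two blinded assessors", at baseline, at completion and 6 months later. The assessors are the only people described as blinded.

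On the schedule, the 20 runners train "2 sessions per week, for 24 weeks", with 30 minutes of stretching and 60 minutes of running per session. The 10 controls train "1 session per week, for 24 weeks", with 60 minutes of stretching.

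**The concern.** The diary and the outcome it feeds do not describe the same events. As worded, the diary yields events that the participant connected with training, whereas the outcome list has no such limit. The judgement of cause is made by a participant who knows the arm, at the moment of deciding whether to write anything down. An event left out leaves no trace, so relatedness cannot be reassessed later and no analysis can repair the loss.

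Two things follow. Non-fall events are under-recorded relative to the listed outcome even if both arms attribute alike. If they attribute differently, the recorded difference between arms partly reflects attribution and not harm. This matters because injury, soreness and need for medical care are the listed safety information on running in a population for which the Background section says there was no evidence on regular intensive running.

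**Working it through.** **Step 1: compare the recording rules with the outcome.**

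| Component | Diary rule (Method) | Outcome (Secondary outcomes) |
|---|---|---|
| Falls | Recorded whatever the cause, through training and 6-month follow-up | No causal condition |
| Injury, muscle soreness | Recorded only if linked to training | No causal condition |
| Pain | Recorded only if linked to training | Not listed |
| Need for medical intervention | Not mentioned | No causal condition |

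The diary is narrower than the outcome on cause. It is not narrower on every event type, since it names pain, which the outcome list omits. Falls are unaffected.

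**Step 2: is different attribution plausible?** Supervised exposure to which an event could be linked, from the Method section:

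- Runners: 2 × 24 = 48 sessions; 30 + 60 = 90 minutes each; 48 × 1.5 h = 72 h.
- Controls: 1 × 24 = 24 sessions of 60 minutes; 24 × 1 h = 24 h.
- Ratio: 72 / 24 = 3.

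This makes a difference plausible but does not prove one. Self-practice is not counted, as its amount is unknown.

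**Step 3: how large could the distortion be?** The Protocol gives no event rate and no attribution rate, so all rates here are assumptions. Let *p* be the true risk, equal in both arms, and *a* the probability that a participant links an event to training and so records it.

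Recorded risk = *p* × *a*; spurious difference = *p* × (*a*_run − *a*_ctrl).

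With *p* = 0.50, 10 of 20 runners and 5 of 10 controls truly have an event:

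| *a*_run | *a*_ctrl | Recorded, runners | Recorded, controls | Spurious difference |
|---|---|---|---|---|
| 0.90 | 0.90 | 0.45 (9 of 20) | 0.45 (4.5 of 10) | 0 |
| 0.90 | 0.60 | 0.45 (9 of 20) | 0.30 (3 of 10) | +15 points |
| 0.90 | 0.30 | 0.45 (9 of 20) | 0.15 (1.5 of 10) | +30 points |
| 0.60 | 0.90 | 0.30 (6 of 20) | 0.45 (4.5 of 10) | −15 points |

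Participants with an event but no record: runners 10 − 9 = 1 in the first three rows and 10 − 6 = 4 in the last; controls 5 − 4.5 = 0.5, 5 − 3 = 2, 5 − 1.5 = 3.5, and 0.5 again in the last row.

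For other true risks with an attribution gap of 0.30: 0.20 × 0.30 = 0.06 and 0.80 × 0.30 = 0.24, so 6 to 24 points. The spurious risk ratio depends only on *a*_run / *a*_ctrl: 0.90 / 0.60 = 1.5 and 0.90 / 0.30 = 3.0.

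**Step 4: with the filter removed.** Setting *a* = 1 in both arms gives a spurious difference of *p* × (1 − 1) = 0.

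**The case against.** The strongest reply is that the two sections need not conflict. The outcome list is a short line that says nothing about cause, and the diary instruction may simply spell out what was meant: tolerability of the training. Under that reading, more events among people who train three times as long are signal. This reading is possible, but the text does not state it. The outcome line also puts falls beside the other events, including falls in the 6 months before training, which training cannot have caused. And even if training-related events are the target, leaving the judgement to participants who know their arm, with no record of what they excluded, is a poor way to measure them.

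A second reply is that the diary is not the only source. Pre-training falls must come from elsewhere, the need for medical intervention is not in the diary sentence, and the assessors might ask about adverse events at their visits. This stands in part: other routes are not excluded. But the Protocol describes no such questioning, and two visits after baseline would rely on recall over about 24 weeks and then about 6 months, a weak substitute for a diary collected monthly.

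Third, the bias figures rest on no figure from the document, the 72 and 24 hours omit self-practice, and no formal comparison of adverse events is stated. All of this stands. The figures show what could happen, not what will, and with 20 and 10 participants any comparison is largely descriptive.

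**Conclusion.** The concern holds. The Protocol fixes a recording rule narrower on cause than the outcome it feeds, and leaves it to unblinded participants to apply. Loss of events not linked to training follows from the rule as written. Bias between arms follows only if attribution differs by arm, and it can go either way.

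Under the assumed rates above, the spurious difference runs from −15 to +30 points and includes 0. These values assume equal true risk in both arms and no other effective source of non-fall events. One control participant is 1/10 = 10 points and one runner 1/20 = 5 points, so a few missing entries change how the result reads.

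The weight is modest. The point concerns the non-fall part of a secondary outcome and leaves the primary outcomes, falls and sample size as they are. It should be corrected because the correction is cheap and lost entries cannot be recovered. Confidence is medium, given the other possible reading of the outcome line.

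**What to change.** In the Method section, strike the relatedness condition from the diary sentence. Ask participants in both arms to record every adverse event whatever its suspected cause, throughout training and the 6-month follow-up, as is already done for falls. Use one identical checklist in both arms covering pain, injury, muscle soreness and whether medical intervention was required. The diary and the outcome list then agree on cause.

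Report all-cause events by arm, with events judged related to training shown as a subset. Existing study staff should judge relatedness afterwards, blinded to arm where feasible. If training-related events are the real interest, that subset supplies them without discarding the rest.

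The cost is a change of diary wording, more entries to transcribe for 30 participants and some staff time for the relatedness judgement. No visit or sample size changes. The wording should be settled before diaries are issued. Self-report by unblinded participants remains a limitation: the change removes the relatedness filter, not every way in which reporting can depend on arm.
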